5.2 RESEARCH ANALYTICS QUALITY CONTROL VARIABLES/OUTCOMES

- de novo metastatic disease
- disease free interval (discontinuation of adjuvant to initiation of 1L)
- number of cycles received in 1L
- proportion of patients who discontinued 1L therapy
- proportion of responses to variables with missing/unknown levels

5.3 10% SAMPLE QUALITY CONTROL VARIABLES

- AJCC stage
- date of initiation of 1L therapy
- provider assessed response to therapy (CR, PR, SD, PD) to 1L therapy

5.4 DISEASE RESPONSE TO THERAPY

For this analysis, beyond the variables considered in section 5, non time-to-event clinical outcomes of interest will include the objective response rate (ORR), which is defined as the sum of CR+PR and clinical benefit rate (CBR), which is defined as the sum of CR+PR+SD (lasting >24 weeks). Both the ORR and CBR will be evaluated according to the provider assessed response to therapy.

5.5 PROGRESSION RATE AND PROGRESSION-FREE SURVIVAL

Disease progression is taken to have occurred when a pathology report or radiological scan note indicates disease progression and/or there is a physician progress note consistent with that determination. Providers will be informed of these criteria and indicate the date of disease progression during initial endocrine therapy for MBC following that guidance.

5.6 SAFETY ENDPOINTS

Not applicable

6 HANDLING OF MISSING VALUES

The eCRF is designed in a way to minimize missing values as much as possible. In situations where the data is truly missing or has inconsistencies (e.g., dates do not follow a logical sequence of events), Cardinal Health will reach out to the providers of these records to validate these fields. In cases where fields cannot be validated, Cardinal Health will consult with Pfizer to determine if the variable should be encoded as unknown, removed or if the subject associated with this variable should be excluded from the study.

7 STATISTICAL METHODOLOGY AND STATISTICAL ANALYSES

7.1 DESCRIPTIVE ANALYSIS

All categorical or numeric non time-to-event variables collected from the chart data abstraction or calculated from said data will be analyzed using descriptive statistical techniques. For demographic continuous variables, the mean, standard deviation, median, and minimum/maximum will be calculated as appropriate. For categorical variables, frequencies and percentages will be provided. The number of missing or unknown observations will be described for both categorical and numeric variables. The 95% confidence intervals will be provided as a measure of estimated precision when appropriate. The following characteristics will be described using in each cohort using the statistical techniques previously described: demographics, receipt of and treatment received for neo/adjuvant treatment, clinical characteristics at diagnosis (e.g., stage, nodal status, menopause status), and clinical characteristics at diagnosis of locoregional recurrent or metastatic/initiation of 1L treatment (e.g., comorbidities, ECOG-PS, menopause status, receipt of CBC/cardiac tests in 30 days prior to initiation of 1L). Other descriptive analyses will include assessing the time from diagnosis to the initial initiation of 1L, duration of adjuvant treatment, and duration of follow-up from initiation of 1L treatment.

In addition, during 1L treatment, the following will be described: dose reductions, dose increases, treatment interruptions, and number of palbociclib cycles completed. The following details the assessment of these outcomes. Response levels are those specified in the case report form for the study.

1. Frequency of initiation of 1L palbociclib at 125mg, 100mg, and 75mg
CCI
[REDACTED]
2. Frequency/proportion of patients with any dose reductions and any dose increase
3. Frequency of reported rationale(s) for dose reduction (toxicity, other) and dose increases (no response, suboptimal response, loss of response, disease progression, other)
4. Mean months from initiation of 1L treatment to first dose reduction, first dose increase
5. Frequency of any treatment interruption; mean number of treatment interruptions during 1L treatment
6. Frequency of reported rationale(s) for first treatment interruption (toxicity, no response, loss of response, disease progression, prepare for alternative treatment strategy, patient choice, other)
7. Mean time to first treatment interruption
8. Mean duration (days) of first treatment interruption

Treatment Discontinuation and Switching:

9. Frequency/proportion of patients who discontinued 1L at 3 month intervals (through 24 months)
10. Frequency of reported rationale(s) for discontinuation of 1L (scheduled duration of therapy completed, disease progression, toxicities/adverse events, patient request (not due to toxicity/adverse event/intolerability), pill burden/compliance, death, unknown, other)
 - a. Frequency of reported rationale(s) for patient request to discontinue therapy (quality of life, difficulty in attending to activities of daily living, no longer wishes to receive treatment, return to work, caregiver burden, financial challenges, unknown, other)
11. Frequency/proportion of patients not initiating subsequent therapy
12. Distribution of regimens received in second-line among patients who received subsequent therapy

Finally, the following variables and outcomes will be described to evaluate disease response rates among each cohort during 1L treatment.

1. Frequency/proportion of patients with disease response assessed
 - a. Frequency/proportion with disease response assessed but recorded response level not available in the medical chart

2. Frequency/proportion of patients experiencing a CR, PR, SD, PD among all patients (including patients for who response was not evaluable/available at the time of data cut off)
3. Frequency/proportion of patients experiencing objective disease response (CR or PR)
4. Frequency/proportion of patients experiencing clinical benefit (CR or PR or SD lasting >24 weeks)
5. Time to response assessment among patients with known response categorization

Outcomes (response rates) for therapies received following discontinuation of 1L treatment will also be reported

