8.3. Variables

For purposes of this study, a regimen will be defined as one or more anti-cancer agents given in combination, over a period of time. Providers will be informed as to the definition of a regimen *but will make the determination themselves as to what constituted a line of therapy in the advanced/metastatic setting*. However, re-assignment of the lines of therapy in the metastatic setting may occur during data analysis based on the dates regimens were initiated and discontinued and the rationale for that discontinuation. For example a patient treated with palbociclib+LET who discontinued palbociclib but continued with LET may be indicated as a single line by the provider but the use of LET monotherapy may be recoded as a subsequent line of therapy during the analysis phase. All dates of initiation and discontinuation of individual agents when received in combination will be abstracted by the patient's treating physician.

Additionally, disease progression is taken to have occurred when a pathology report or radiological scan note indicates disease progression and/or there is a physician progress note consistent with that determination. Providers will be informed of these criteria and indicate the date of disease progression as recorded in the patient charts during initial endocrine therapy for MBC following that guidance.

The table below describes data elements to be abstracted by the provider (“Abstracted Data Points”) and independent/exposure variables calculated from the abstracted data (“Calculated Variables”).

Variable	Operational definition
Patient demographics	Abstracted Data Points: Year of birth, payer, state of residence, ethnicity, weight, height, ER status, PR status, HER2 status, family history of breast cancer. Calculated Variables: age at advanced/metastatic diagnosis, age at initiation of endocrine-based therapy, body mass index.
Clinical characteristics	Abstracted Data Elements: date of initial breast cancer diagnosis, date of diagnosis of advanced/metastatic disease, AJCC stage, node status, menopause status, ECOG-PS (@ treatment for advanced/metastatic disease), sites of metastatic disease (@ initiation of treatment for advanced/metastatic disease), comorbidities (@ initiation of treatment for advanced/metastatic disease). Calculated Variables: time to advanced/metastatic disease, Charlson comorbidity index.

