8.7. Data Analysis

Detailed methodology for summary and statistical analyses of data collected in this study will be documented in a SAP, which will be dated, filed and maintained by the sponsor. The SAP may modify the plans outlined in the protocol; any major modifications of primary endpoint definitions or their analyses would be reflected in a protocol amendment.

Beyond the variables described in [Section 8.3](#), non time-to-event clinical outcomes of interest include the ORR and clinical benefit rate (CBR) (CR+PR+SD lasting >24 weeks). The ORR and CBR will be evaluated according the provider assessed response to therapy.

Additionally, providers will also enter the data of disease progression into the eCRF (or discontinuation due to toxicity or other rationale) as reported in the patient charts. PFS and/or time to progression will be assessed at 6-, 12-, 18-, and 24-month following the initiation of therapy (survival rates will also be reported separately).

All categorical or numeric non time-to-event variables collected from the chart data abstraction or calculated from said data will analyzed using descriptive statistical techniques. For numeric variables, the mean, standard deviation, median, and minimum/maximum will be calculated as appropriate. For categorical variables, frequencies and percentages will be provided. The number of missing or unknown observations will be described for both categorical and numeric variables. The 95% confidence intervals will be provided as a measure of estimated precision when appropriate. Comparisons of categorical variable will be made using Chi-square tests (or Fisher exact test) while the student's T-test (or Wilcoxon rank-sum test), F-test or other non-parametric equivalent test will be used to compare values for numeric variables. Statistical significance will be determined using a two-sided $\alpha=0.05$. For univariate comparisons of proportions, any analysis resulting in less than 5 individuals in any cell will not be performed. Similarly, the minimum number of patients to conduct an analysis comparing means of some continuous variable is 30 patients.

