2.4 STUDY OBJECTIVES

Primary Objectives

Among MBC patients receiving palbociclib+LET according to its labeled indication as initial endocrine therapy for MBC, the research objectives are to:

- 1) Describe the demographic and clinical characteristics of patients
 - a. Demographic characteristics will include age, race/ethnicity, body mass index, insurance status, state of residence at the date of MBC diagnosis, and palbociclib initiation. Employment status will be assessed to the extent documented in the

record. Overall duration of follow-up (months) from the initiation of palbociclib+LET will be presented.

b. Clinical characteristics will include year of breast cancer and MBC diagnosis, AJCC stage at initial diagnosis, sites of metastatic disease at MBC diagnosis and palbociclib+LET initiation (including nodal status), menopausal status at MBC diagnosis and initiation of palbociclib+LET, verification of HER2 and ER/PR status, ECOG performance status, comorbidities (based on Charlson comorbidity index listing) at initiation of palbociclib+LET, and treatments received in the neoadjuvant or adjuvant setting (chemotherapy, hormone therapy, surgery, radiation therapy).

2) Describe the frequency of laboratory monitoring during treatment

- a. Note that complete blood count (CBC) monitoring and cardiac function monitoring will be assessed, but lab results/values will not be assessed under this objective.
- b. Evaluate the extent of laboratory monitoring using CBC during the first three cycles of 1L treatment
- c. Assess the frequency of cardiac toxicity monitoring using electrocardiogram, liver function panels, and electrolytes during the first three cycles of 1L treatment
 - i. The frequency of assessment of cardiac monitoring by each method will be evaluated during the initial endocrine-based therapy for MBC

3) Describe treatment patterns in terms of palbociclib+LET dosing, cycles received, and post-discontinuation treatment regimens

- a. Palbociclib dosing will include description of the starting dose, dose adjustment (increase and decrease, interruptions), time to dose adjustment for palbociclib, and rationale for dose adjustment (provider interpretation)
- b. Duration of palbociclib in terms of the number of cycles completed prior to the discontinuation of initial treatment for MBC
- c. Primary rationale for the discontinuation of palbociclib+LET per provider interpretation

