7.2 SURVIVAL ANALYSIS

[figure not shown]
Survival analysis, also called time to event analysis, will be used in the current research to estimate the time to treatment discontinuation, time to progression, and PFS in 1L. This method of analysis is employed when non-informative right-censoring occurs as is the case for this study since not all patients will have discontinued treatment, progressed or died by the end of the study period. The Kaplan-Meier method (product limit estimator) will be used to generate median estimates of time to progression and PFS if median time is reached within the population. Survival curves will also be generated. In addition to calculating the median survival estimate, the life-table method will be used to estimate these time to event outcomes at successive 3 month intervals through 24 months post initiation of 1L.

The following lists the measurements to be conducted using survival analysis techniques:

1. Median time to treatment discontinuation
 - a. Proportion of patients (survival estimate and 95% confidence interval) who are still receiving 1L treatment at 3, 6, 12, 18, and 24 months post 1L initiation
 - b. Event = any treatment discontinuation for any reason, censor = patients who are still on 1L therapy at data cut-off
2. Median time to progression
 - a. Proportion of patients (survival estimate and 95% confidence interval) who are progression free at 3, 6, 12, 18, and 24 months
 - b. Event = any treatment discontinuation for disease progression, censor = patients who are still on 1L therapy or who discontinued therapy for any reason other than disease progression at data cut-off
3. Median progression-free survival
 - a. Proportion of patients (survival estimate and 95% confidence interval) who are progression free and alive at 3, 6, 12, 18, and 24 months

- b. Event = any treatment discontinuation for disease progression or death, censor = patients who are still on 1L therapy or who discontinued therapy for any reason other than disease progression or death at data cut-off
- 4. Proportion of patients alive at 3, 6, 12, 18, and 24 months following 1L initiation
 - a. Event = death, censor = date of last follow-up among patients who are not deceased

CC
I

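### Palbociclib duration in cycles (objective 3b) is planned as a plain summary, with no stated denominator and no censoring of patients still on treatment

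*SAP*

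**What the plan says.** Objective 3b, worded alike in Protocol 7.1 and SAP 2.4, is "Duration of palbociclib in terms of the number of cycles completed prior to the discontinuation of initial treatment for MBC". SAP 2.4 lists it under the primary objectives.

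SAP 7.1, which covers variables that are not time-to-event, says only that "dose reductions, dose increases, treatment interruptions, and number of palbociclib cycles completed" will be described. The visible numbered list that follows has no item for cycles. SAP 7.1 names its summary statistics for demographic continuous variables; Protocol 8.7 is wider: "For numeric variables, the mean, standard deviation, median, and minimum/maximum will be calculated as appropriate". SAP Table 2 holds one field for total cycles received and does not define it for a patient still on drug. SAP section 6 deals with missing or inconsistent fields, not with ongoing treatment.

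SAP 7.2 justifies survival methods "since not all patients will have discontinued treatment, progressed or died by the end of the study period". Its item 1 estimates time to first-line discontinuation with this rule: "Event = any treatment discontinuation for any reason, censor = patients who are still on 1L therapy at data cut-off". SAP objective 5a adds persistence on the initial regimen at 3, 6, 12, 18 and 24 months.

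On lines of therapy, Protocol 8.3 notes that "a patient treated with palbociclib+LET who discontinued palbociclib but continued with LET may be indicated as a single line by the provider". The same sentence goes on to allow, but not require, the letrozole-only period to be recoded as a later line at analysis. SAP 2.3 leaves the definition of a line to the provider and does not mention recoding.

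**The concern.** The plan recognises right-censoring for first-line treatment time but not for the cycle count that it also calls a duration. Two readings are open. The wording of 3b points to patients who have stopped; the wording of SAP 7.1 fits all patients, counted to date. The first leaves out the patients treated longest. The second credits ongoing patients with only what they had received by cut-off.

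Without a rule, the reported number depends on how recently patients started and on which denominator the programmer picks. Mixed follow-up is plausible: the minimum is one month, and SAP 2.1 asks for random selection from the eligible pool, whereas Protocol 8.1 asks for consecutive patients from the earliest. A reader would take the result as how long patients stay on palbociclib in practice.

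**Working it through.** The plan gives no expected cycle count, so there is no figure to reproduce. The check asks what each reading would return when the true duration is known.

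**Inputs from the documents.** Target of 200 patients (SAP 2.1). Minimum follow-up of 1 month (SAP Table 1). Treatment on or after 03 February 2015 (Protocol abstract), at least 3 months after the provider's first use (Protocol 8.2.1), and data collection from Q1 2019: 03 May 2015 to 31 March 2019 is 46.9 months, taken as 47. Protocol section 6 cites a trial median PFS of 24.8 months and a real-world study with 64.3% progression-free at 24 months. Under an exponential curve the latter implies a median of 24 × ln 2 / −ln 0.643 = 37.7 months.

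**Assumptions not in the documents.** Exponential time on drug T with median m; PFS used as a stand-in for time on drug in the 24.8 and 37.7 cases; 15 and 20 months as lower cases; 28-day cycles, so cycles = months × 30.4375/28 = months × 1.0871; follow-up F uniform from a to b months and independent of T.

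**Formulas.** Let S(t) = 2^(−t/m), λ = ln 2 / m, and G(t) = 1 for t ≤ a, (b − t)/(b − a) afterwards.
- True median in cycles = m × 1.0871.
- To-date median: solve S(u) × G(u) = 0.5.
- Fraction seen to stop by u (for u > a): I(u) = 1 − S(u)G(u) − [S(a) − S(u)] / [λ(b − a)].
- Stopped-only median: solve I(u) = I(b)/2.

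**Worked case, m = 20, follow-up 1 to 47.** λ(b − a) = 0.03466 × 46 = 1.594; S(1) = 0.966; S(47) = 0.196.
- I(47) = 1 − (0.966 − 0.196)/1.594 = 0.517, so 48% are still on drug.
- Stopped-only: I(u) = 0.2586 at u = 9.48 months, or 10.3 cycles.
- To-date: at u = 12.06, S = 0.658 and G = 34.94/46 = 0.760, product 0.500; 12.06 months is 13.1 cycles.
- True: 20 × 1.0871 = 21.7 cycles.

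**Median cycles, all cases**

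| True median, months (cycles) | 1–47 months: stopped-only | 1–47: to-date | 24–47 months: stopped-only | 24–47: to-date |
|---|---|---|---|---|
| 15 (16.3) | 9.2 | 11.1 | 12.0 | 16.3 |
| 20 (21.7) | 10.3 | 13.1 | 13.5 | 21.7 |
| 24.8 (27.0) | 11.1 | 14.7 | 14.5 | 26.4 |
| 37.7 (41.0) | 12.2 | 17.5 | 16.1 | 30.2 |

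With follow-up of 12 to 47 months and m = 20, the two medians are 11.6 and 17.7. The to-date median is exact where every patient is followed past the true median, because G is then still 1. It fails again at 37.7 months even with at least 24 months of follow-up.

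**Means, m = 20.** Restricted mean to 47 months = (20/0.6931) × (1 − 2^(−47/20)) × 1.0871 = 25.2 cycles. With 1 to 47 months the stopped-only mean is 13.0 and the to-date mean 16.2; with 24 to 47 months they are 15.5 and 22.0. The to-date mean stays low even where the to-date median does not.

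**Sampling error, n = 200, m = 20 (simulation).** With 1 to 47 months, 95% of to-date medians fall in 10.9–15.7, below the true 21.7. A Kaplan-Meier median on the cycle scale centres on 21.8 (17.2–27.7). With 24 to 47 months, 95% of stopped-only medians fall in 10.8–16.4.

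**Shape.** Weibull times with the same 20-month median and shape 0.8 or 1.3 give, for 1 to 47 months, stopped-only medians of 8.0 or 13.1 and to-date medians of 12.3 or 14.1. The direction does not depend on the exponential form.

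**SAP 7.1 item 9 (minor).** If computed over all patients, the 24-month figure at m = 20 with 1 to 47 months is I(24) = 1 − 0.4353 × 0.5 − (0.966 − 0.4353)/1.594 = 45.0%, against a true 1 − 2^(−24/20) = 56.5%. With at least 24 months of follow-up there is no gap.

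**The case against.** The strongest reply is that the plan already measures duration properly. SAP 7.2 item 1 censors ongoing patients, and objective 5a ends persistence at a regimen change, which could include dropping palbociclib. If letrozole alone is recoded as a later line, stopping palbociclib is first-line discontinuation and item 1 is the censored duration of palbociclib in months. This stands, and it confines the problem to the cycle scale. A reader might infer that the plan ignores censoring of treatment duration altogether; the documents do not support that. It does not close the gap: recoding is optional, SAP 2.3 does not mention it, and neither analysis gives a censored result in cycles.

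Second, cycles received to date and cycles among stopped patients are both true facts about exposure. That also stands: either is a valid description if labelled. The understatement arises when an unlabelled figure is read as the cohort's duration, which is how 3b presents it.

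Third, the 1 to 47 month case is the least favourable. Selecting consecutive patients from the earliest, as in Protocol 8.1, would lengthen follow-up, and the to-date median could then be right. This is fair for the to-date median at true medians up to about 24 months. It does not rescue the stopped-only summary.

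Fourth, denominators often sit in table shells, which the milestones list as a deliverable and which are not in the documents. Text in SAP 7.1 and after 7.2 item 4 is also redacted. The point is therefore limited to the visible text.

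**Conclusion.** The point holds for the cycle-scale summary of objective 3b. Under the stated assumptions, a stopped-only median falls short of the cohort's duration in every case: 9.2 to 12.2 cycles against 16.3 to 41.0 with 1 to 47 months of follow-up, and 12.0 to 16.1 with 24 to 47 months. A to-date median is 11.1 to 17.5 with the shorter follow-up. With 24 to 47 months it is right or nearly so up to a true median of 24.8 months, and low (30.2 against 41.0) at 37.7. These sizes illustrate the problem; they do not forecast the study's result. They rest on an assumed distribution, cycle length and follow-up pattern.

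Two stronger readings are not supported. The to-date median is not always biased. Items 4, 7 and 9 of SAP 7.1 are not shown to be wrong: item 9 names no denominator and could be drawn from the life table, and items 4 and 7 can only be means among patients who had the event. Those are matters of labelling and consistency.

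The matter should be settled before tables are programmed. It does not threaten the censored analyses in SAP 7.2.

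**What to change.** 1. Report palbociclib cycles by Kaplan-Meier on the cycle scale: the event is palbociclib stopped for any reason, and ongoing patients are censored at cycles to date. Give the number ongoing. Since interruptions make cycles accrue at different rates, show the result next to SAP 7.2 item 1.
2. Label any plain summary of cycles as either among discontinued patients or cycles to date, with n.
3. Minor: take SAP 7.1 item 9 from the 7.2 item 1 analysis, where "the life-table method will be used to estimate these time to event outcomes at successive 3 month intervals through 24 months", so that the two cannot disagree. Label items 4 and 7 as among patients with the event before cut-off, with n.

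The cost is SAP wording and an extra table. Total cycles are already a field in SAP Table 2, and Protocol 8.3 states that "All dates of initiation and discontinuation of individual agents when received in combination will be abstracted", so no new data should be needed. The differing descriptions of patient selection in Protocol 8.1, the Protocol abstract and SAP 2.1 determine how large the bias could be, and should be reconciled separately.

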7. RESEARCH QUESTION AND OBJECTIVES

The main objective of this study is to describe patient demographics, clinical characteristics, toxicity monitoring, treatment patterns and clinical outcomes among postmenopausal, female, HR-positive, HER2-negative, MBC patients receiving palbociclib+LET as initial endocrine therapy. Demographic and clinical characteristics and outcomes will be presented overall, and among groups for the following three planned primary grouping variables:

1. Visceral vs. non-visceral at the initiation of initial endocrine therapy for MBC.
2. Received prior neo/adjuvant endocrine therapy versus no prior neo/adjuvant therapy.
3. De novo metastatic disease versus ≤ 12 months disease free interval since prior neo/adjuvant treatment versus > 12 months disease free interval since prior neo/adjuvant treatment.

[figure not shown]

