8.2.1. Inclusion Criteria

Patients must meet all of the following inclusion criteria to be eligible for inclusion in the study:

1. Diagnosed with locoregional recurrent or metastatic female breast cancer.
2. Pathologically confirmed HR-positive/HER2-negative diagnosis.
3. Received treatment with palbociclib in combination with letrozole as initial endocrine-based therapy for advanced/metastatic breast cancer:
 - a. Initiated treatment with palbociclib at least 3 months following the provider's first use of palbociclib following its FDA approval.
 - b. At least 1 month of follow-up (at least one visit with the provider) after initiation of palbociclib.
4. Postmenopausal (or receiving surgical or medical treatment to induce menopause) at the time of initiation of palbociclib.
5. ≥ 18 year old at initiation of palbociclib.

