2.1 STUDY POPULATION

CCI

[REDACTED]

- 1) Patients treated with palbociclib+LET as initial endocrine therapy for MBC per the palbociclib U.S. FDA approval label;

CCI

[REDACTED]

The target sample size for each of the three cohorts is 200 patients. Table 1 illustrates the selection criteria for each of the cohorts. Patients must meet all of the following inclusion criteria to be eligible for inclusion in the study. No exclusion criteria will be imposed for the selection of patients.

Table 1. Cohort Selection Criteria.

Palbociclib+LET	CCI
Diagnosed with locoregional recurrent or metastatic female breast cancer	
Pathologically confirmed HR-positive/HER2-negative tumor	
Received treatment with palbociclib in combination with LET as initial endocrine-based therapy for advanced/metastatic breast cancer 
 - Initiated treatment with palbociclib at least 3 months following the provider's first use of palbociclib after 03 Feb 2015 - At least 1 month of follow-up data after initiation of palbociclib 	
Postmenopausal (or receiving surgical or medical treatment to induce menopause) at the time of initiation of 1L treatment for locoregional recurrent or BMC	
≥18 year old at initiation of endocrine therapy	

Patient eligibility will be confirmed by the treating physician. Providers may complete a maximum of 20 eCRFs. Providers will be asked to randomly select patients from the pool of eligible patients and verify that they have performed random patient selection.

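### Dose changes and interruptions (SAP 7.1, items 2, 4, 5 and 7) are summarised without allowing for unequal follow-up and time on treatment; landmark time-to-first-event estimates should be added to SAP 7.2

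*SAP*

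**What the plan says.** SAP 7.1 lists the 1L dosing summaries. Item 2 is "Frequency/proportion of patients with any dose reductions and any dose increase". Item 5 is "Frequency of any treatment interruption; mean number of treatment interruptions during 1L treatment". Timing is covered by item 4, "Mean months from initiation of 1L treatment to first dose reduction, first dose increase", and item 7, "Mean time to first treatment interruption". None of the four has a window, a person-time denominator or a rule for patients without the event.

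SAP 7.2 uses survival methods "to estimate the time to treatment discontinuation, time to progression, and PFS in 1L", and its list of measurements adds survival. Dose changes and interruptions are not on that list. Yet Protocol 7.1, Objective 3a, includes time to dose adjustment, and the Protocol abstract names Kaplan-Meier for PFS and for other time-to-event analyses.

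On follow-up, SAP 2.1 requires "At least 1 month of follow-up data after initiation of palbociclib", and Protocol 8.2.1 says the same. The Protocol abstract allows starts from 03 February 2015 and begins data collection in Q1 2019. On grouping, Protocol section 7 states: "Demographic and clinical characteristics and outcomes will be presented overall, and among groups for the following three planned primary grouping variables". The groups are defined by visceral disease, prior neo/adjuvant endocrine therapy, and de novo disease or disease-free interval.

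**The concern.** A patient followed for two months, or who stops 1L at month three, has little opportunity for a later dose change. An any-event proportion over all patients therefore mixes the risk of a dose change with the time available to observe one. Two sources of unequal time are present: calendar follow-up, set by when the patient started, and time on 1L, set by progression, toxicity or choice.

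The first affects the overall figure. Patient selection is described as consecutive from the earliest case in Protocol 8.1 and as random in SAP 2.1, so the mix of early and recent starters is not settled. The second matters if groups that stay on treatment for different lengths of time are set side by side: the longer-treated group would show more reductions and more interruptions at the same monthly risk. Items 4 and 7 do not repair this, because a plain mean can be taken only over patients who had the event, and it too grows with time observed.

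Dosing is a stated objective, and SAP 7.2 already handles right-censoring for other endpoints in the same patients.

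**Working it through.** The documents give no expected dose-change rate and no treatment duration by subgroup, so there is no plan figure to reproduce. What follows is an illustration on stated assumptions.

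**Inputs**
- From the documents: minimum follow-up 1 month. The earliest start, 03 February 2015, plus the 3-month provider run-in gives early May 2015, and from there to early January 2019 is about 44 months.
- Assumed: follow-up uniform over 1-44 months; hazard of first reduction h(t) = 0.04 per month to month 6, then 0.01; 0.08 interruptions per month; exponential time on 1L with rate λ = ln 2 / median. All risks are identical in every group.
- Assumed medians on treatment: 10, 14.5, 24.8 and 35 months. The values 14.5 and 24.8 appear in Protocol section 6, but as trial-arm PFS medians, not subgroup treatment times. The values 10 and 35 are in neither document.

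**Crude proportion.** P = ∫ h(t) · exp(−H(t)) · exp(−λt) · G(t) dt, where H is the cumulative hazard and G(t) the probability of follow-up beyond t. Mean interruptions = 0.08 × mean observed months on 1L.

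| Median on 1L (months) | Any reduction | Mean observed months on 1L | Mean interruptions | Mean months to first reduction, events only |
|---|---|---|---|---|
| 10 | 20.8% | 10.14 | 0.81 | 4.7 |
| 14.5 | 23.2% | 12.46 | 1.00 | 5.5 |
| 24.8 | 26.1% | 15.53 | 1.24 | 6.4 |
| 35 | 27.6% | 17.17 | 1.37 | 6.9 |

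Gaps at identical risk: 26.1 − 23.2 = 2.9 points, and 27.6 − 20.8 = 6.8 points. The last column shows that item 4 shifts as well.

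**Effect of follow-up alone** (median 24.8 months on 1L): follow-up uniform over 1-12 months gives 17.3%; over 24-44 months, 31.0%.

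**Sensitivity to the assumptions.** A second set of scenarios used Weibull hazards (12-month risk 20%, 30% or 40%; constant or front-loaded, shapes 1, 0.5 and 0.25), medians of 12, 14.5 or 18 against 24.8 months, and a cut at 24 or 36 months. The gap ran from 0.7 to 14.3 points, always higher in the longer-treated group, and smallest when reductions cluster early and the medians are close.

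**Which estimator removes the artefact?** Under the first set of assumptions:

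| Month | Competing-risk incidence, median 10 | Competing-risk incidence, median 35 | Kaplan-Meier target 1 − exp(−H), both groups |
|---|---|---|---|
| 6 | 17.6% | 20.2% | 21.3% |
| 12 | 20.1% | 24.0% | 25.9% |
| 24 | 22.6% | 29.9% | 34.3% |

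For example, at 12 months H = 0.04×6 + 0.01×6 = 0.30, and 1 − exp(−0.30) = 25.9%. Competing-risk incidence with discontinuation as the competing event does not depend on follow-up (19.7% at 6 months with median 24.8 on 1L, whatever the follow-up). It still differs by 29.9 − 22.6 = 7.3 points at 24 months, no less than the crude gap of 6.8. Censoring at discontinuation gives the same target in both groups.

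**Rates per month.** A single rate is safe only if the hazard is roughly constant. With 12-month risk 30%, medians 12 and 24.8, and a 36-month cut, first reductions per 100 patient-months were 2.97 in both groups under constant hazard, but 2.68 and 2.27 under shape 0.5.

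**The case against.** The strongest reply has three parts.

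First, the study is descriptive, and the share of patients with any reduction during 1L correctly describes what happened. Follow-up, cycles completed and time to discontinuation are reported as well, so a reader can see the exposure. This stands: the crude figures are not wrong, and no safety endpoint rests on them (SAP 5.6 and 7.5). But separate exposure summaries do not let a reader recover a risk by month 6 or 12, and time to dose adjustment is itself an objective.

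Second, a reader might infer that the plan will produce false tolerability differences between the Protocol section 7 groups. The documents do not establish that. The grouping sentence names demographic and clinical characteristics and outcomes; it leaves out treatment patterns, the heading under which dosing falls. SAP 7.1 does call the dosing items outcomes, but the wording is general, and the SAP text introducing the groups is partly redacted. Subgroup display of these items is therefore an inference.

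Third, the size depends on chosen medians. This also stands. With 14.5 and 24.8 months the gap is about 3 points, and with an assumed 100 patients per group a two-sided 0.05 test would reject about 8% of the time.

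A reader might also think that competing-risk incidence is the natural remedy for a subgroup comparison. The table above shows that it leaves the time-on-treatment difference in place.

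**Conclusion.** The point holds in a limited form. Items 2 and 5 are sound as raw counts but are not estimates of the risk of a dose change, and items 4 and 7 share the defect. The overall percentage depends on the sampled mix of follow-up: 17% against 31% in the illustration, at one and the same risk. If the items are shown by subgroup, identical risk could appear as a difference of about 3 points (medians 14.5 and 24.8 months) to about 7 points (10 and 35). The direction follows from the arithmetic, with more events in the longer-treated group. The size rests on assumed hazards, follow-up and treatment durations that the documents do not supply. Severity is low to moderate: a cheap improvement that brings the SAP into line with Objective 3a and the Protocol abstract.

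**What to change.** 1. Add time to first dose reduction, first dose increase and first interruption to the list in SAP 7.2. Give Kaplan-Meier (cause-specific) estimates with 95% confidence intervals at 3, 6, 12, 18 and 24 months, censoring at 1L discontinuation, death or last follow-up. Use these for any subgroup comparison.
2. If an overall descriptive figure is wanted, competing-risk cumulative incidence may be given, since it corrects for unequal follow-up. Do not base subgroup comparisons on it.
3. Report interruptions per patient-month on 1L palbociclib or, if the rate is not roughly constant, as a mean cumulative count by time.
4. Keep items 2, 4, 5 and 7 as a supplement, and label items 4 and 7 as means among patients with the event.
5. State whether the dosing items will be shown by the Protocol section 7 groups.

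**Cost.** SAP wording and one more table. Times to first reduction, increase and interruption are already needed for items 4 and 7; the landmarks are already in SAP 7.2; the censoring dates are in SAP Table 2. A mean cumulative count needs the date of every interruption, so the eCRF should be checked for that. The Kaplan-Meier estimate assumes that discontinuation is independent of dose-change risk. Toxicity could drive both, so the assumption should be stated, with the reasons for discontinuation (SAP 7.1, item 10) shown alongside.
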